7 TREATMENT PLAN

This is a randomized, controlled, open label pilot trial. A total of 60 patients

will be enrolled, with at least 15 patients allocated to each treatment group (Arms C and D constituting the same treatment group). The initial treatment period is 6 months (24 weeks). During the initial treatment period, patients will be randomized to one of 4 arms: HCQ alone (Arm A), EVE alone (Arm B), combination HCQ and EVE (Arm C) – Arm C is closing to accrual with Amendment 7 – or control/delayed combination HCQ and EVE (Arm D). Starting with Amendment 7, patients who would have been allocated to Arm C will be redirected to Arm D in order to increase the number of patients with repeat DTC assessments to aid assay reproducibility analysis. At the conclusion of 3 cycles of therapy (Arms A, B, and C) or 3 cycles of observation (Arm D), patients will undergo repeat bone marrow aspirate. Patients on Arm D will then commence combination therapy with HCQ + EVE for 6 cycles (24 weeks). After 3 cycles of therapy, patients on Arm D will undergo another bone marrow aspirate. After 6 cycles of therapy, patients on all arms will undergo another bone marrow aspirate. Patients with a negative bone marrow aspirate for DTCs at after cycle 6 will have all therapy discontinued and enter the follow up phase. Patients who have persistently positive bone marrow DTCs will be continued on combination HCQ + EVE for an additional 6 cycles (24 weeks). At the conclusion of this combination treatment period (cycle 12), all treatment will be discontinued and a bone marrow aspirate will be performed.

Patients will be evaluated at the initiation of every cycle for adverse events, and dose reductions will be employed for toxicity. Patients will continue to be followed for recurrence events for 3 years after completion of treatment.

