10.11 Data Safety Monitoring Board

In addition to the above safeguards, an independent data safety monitoring committee, consisting of 2 medical oncologists and a member of the patient advocate team will meet with the PI and the study team monthly to review safety data, to assure that no unanticipated safety signals or risks are arising in the conduct of the study. In addition, the DSMB will review interim safety analyses for each arm after every 3 patients have been enrolled. We will implement a Bayesian toxicity monitoring approach with a target protocol-defined DLT rate of 30% as outlined in the statistical plan. This additional safeguard is to ensure that patients on this trial, with potentially curable disease, are being monitored closely.

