12.2 Analysis Plan

12.2.1 Primary Endpoint

The phase II trial endpoint “feasibility” is based upon the overall safety and tolerability of the treatment arms, and will be defined as at least 11 of 15 patients within each treatment group completing 6 cycles of therapy without grade 3 or 4 toxicity. When evaluating feasibility of the combination therapy, Arm C and D may be combined for analysis, since both arms receive the same study treatment (Arm D is just a delayed start). Toxicity will be determined by NCI CTCAE v4 criteria, and categorized by system and grade. Patients who drop out before the 6-month time

point for reasons other than toxicity and not related to feasibility will be replaced. With 15 patients per group, an exact 95% confidence interval around the feasibility and toxicity rates will be no more than 0.52 units wide. Arms that are discontinued for lack of feasibility will be dropped from the trial, but others may continue, so long as they remain “feasible” by this definition.

Because this is a potentially curable patient population, we will also institute an early stopping rule, should the toxicity rates exceed those expected or acceptable in this setting. To do this, we will implement a Bayesian toxicity monitoring approach with a target protocol-defined DLT rate of 30%. We assume a $Beta(1,2)$ prior, equivalent to one DLT observed in 3 treated patients. Early termination for toxicity will be considered based on a posterior probability that the toxicity rate exceeds 30%. Early termination will be considered if DLT is observed in 2 of 3 patients (0.84 posterior probability), 3 of 6 patients (0.81), 4 of 9 patients (0.79), 5 of 12 patients (0.78), 6 of 15 patients (0.78).

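### The toxicity boundaries stop at 15 patients with no stated posterior cut-off, although Arm D can now exceed 15 and about 30 patients are planned for HCQ + EVE.

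*Protocol*

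**What the plan says.** Protocol section 12.2.1 sets a target DLT rate of 30% and a Beta(1,2) prior, described as "equivalent to one DLT observed in 3 treated patients". The criterion is worded as follows: "Early termination for toxicity will be considered based on a posterior probability that the toxicity rate exceeds 30" per cent. No probability threshold is attached. The listed triggers are 2 of 3, 3 of 6, 4 of 9, 5 of 12 and 6 of 15, each with its posterior probability; the last reads "6 of 15 patients (0.78". Nothing follows.

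Section 10.11 has the DSMB "review interim safety analyses for each arm after every 3 patients have been enrolled", sets no upper limit on those looks, and refers to the statistical plan for the rule.

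Section 7 keeps the total at 60, "with at least 15 patients allocated to each treatment group (Arms C and D constituting the same treatment group". It closes Arm C with Amendment 7 and redirects its later allocations to Arm D. Section 7.1 gives Arm D the same HCQ + EVE combination after 12 weeks of observation. Section 12.2.1 allows C and D to be combined when feasibility is evaluated, but says nothing about combining them for toxicity monitoring. The SAP text supplied covers the DTC count model and adds nothing on stopping.

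**The concern.** A monitoring table should reach the largest number of patients planned for the unit it monitors. This one reaches 15. With four arms of 15 monitored separately, it would have been complete. Now that Arm C's remaining allocations go to Arm D, Arm D can grow past the last line. If the regimen is the monitoring unit, the table stops halfway.

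A missing line would matter little if the rule could be continued from its own definition. It cannot, because the cut-off is not stated. At its look at 18 patients the DSMB would have a prior and a target but no agreed trigger, on the two-drug regimen, in a population that section 12.2.1 itself describes as potentially curable.

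**Working it through.** **Inputs.** Prior Beta(1,2), target 0.30 and the five listed boundaries (section 12.2.1); looks every 3 patients (section 10.11); total 60 (sections 7 and 12.1); 15 per arm (synopsis). Assumption: Arms A and B take exactly 15 each. Section 7 says at least 15, so the combination would have fewer than 30 if either takes more.

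**1. Reproduce the plan's figures.** With x DLTs in n patients the posterior is Beta(1 + x, 2 + n − x), and the criterion is P(rate > 0.30).

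| n | Boundary | Protocol | Recomputed | One DLT fewer |
|---|---|---|---|---|
| 3 | 2 | 0.84 | 0.837 | 0.528 |
| 6 | 3 | 0.81 | 0.806 | 0.552 |
| 9 | 4 | 0.79 | 0.790 | 0.570 |
| 12 | 5 | 0.78 | 0.781 | 0.584 |
| 15 | 6 | 0.78 | 0.775 | 0.597 |

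All five agree after rounding.

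**2. What cut-off does the table imply?** Each boundary must meet the cut-off and one DLT fewer must miss it. So the cut-off lies above 0.597 and at or below 0.775, and any value in that interval gives the same five lines.

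**3. Extend the table.** Beyond 15 the lines depend on which value is chosen.

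| Cut-off | n = 18 | 21 | 24 | 27 | 30 |
|---|---|---|---|---|---|
| about 0.60 | 6 | 7 | 8 | 9 | 10 |
| about 0.65 to 0.77 | 7 | 8 | 9 | 10 | 11 |
| 0.775 (lowest listed value) | 8 | 9 | 10 | 11 | 12 |

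The posteriors in the middle row are 0.772, 0.771, 0.770, 0.771 and 0.772. All lie just below 0.775, which is why the bottom row differs.

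**4. How many patients lie beyond the table?** Combination total: 60 − 15 − 15 = 30, both before and after Amendment 7.
- C and D pooled: 30 − 15 = 15 patients, half of the regimen.
- Per arm: Arm D takes 30 − c, so (30 − c) − 15 = 15 − c. That is 15 if c = 0, 9 if c = 6, 3 if c = 12 and 0 if c = 15.

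Replacement of drop-outs under section 12.2.1 could also take an arm past 15; the number is not given.

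**5. Effect of extending.** The figures are the probability of crossing at least one boundary in a single monitored stream, by exact binomial recursion with looks every 3 patients.

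| True DLT rate | By 15 | By 30, 0.77 table | By 30, 0.775 table |
|---|---|---|---|
| 20% | 19.5% | 21.3% | 19.9% |
| 30% | 46% | 55% | 50% |
| 40% | 73% | 86% | 81% |
| 50% | 91% | 98% | 96% |

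At a 40% rate, a stream that passed 15 without a trigger would be caught later with probability (0.860 − 0.734)/(1 − 0.734) = 47% under the 0.77 table, and 27% under the 0.775 table.

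**The case against.** Three readings go further than the documents allow.

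- **Amendment 7 took the regimen to 30.** It did not. The synopsis already has 15 patients in each of four arms, and Arm D receives the combination after observation. The amendment moves patients from C to D; what it changes is the size of Arm D.
- **Half of the combination patients are treated under no boundary.** That holds only if C and D are pooled. Section 10.11 says each arm, and on that reading the shortfall is 15 − c, which is zero if Arm C had filled.
- **Formal protection ends at 15.** Only the listed numbers end there. DSMB looks every 3 patients and monthly safety review continue (section 10.11), the DSMC can recommend suspension or termination (section 10.7), and the research monitor can stop the protocol (section 10.8).

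The strongest statistical objection concerns the comparator. Per-arm monitoring of two full 15-patient combination arms gives two chances to trigger. At a 40% rate at least one arm triggers with probability 1 − (1 − 0.734)² = 93%, above the 86% of a pooled stream followed to 30. The price is more false alarms: 1 − (1 − 0.195)² = 35% at a 20% rate, against 21%. So the rise from 73% to 86% describes one stream followed further. It is not a gain over two complete per-arm streams.

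All of this stands. None of it supplies a cut-off, a monitoring unit for toxicity, or a trigger for an Arm D that passes 15.

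**Conclusion.** The concern holds as a gap between the monitoring rule and the amended design. The rule has no listed boundary after 15 and cannot be extended uniquely from the text, since 6, 7 or 8 DLTs at 18 patients are all compatible with it. The number of patients affected is 15 − c under per-arm monitoring or about 15 of 30 under pooling. This assumes 15 each in Arms A and B, and the documents do not give c.

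For one stream, extending from 15 to 30 patients adds about 13 percentage points of detection at a 40% DLT rate with the 0.77 table (about 7 with the 0.775 table). With the 0.77 table it costs about 2 points at a 20% rate and 9 at the 30% target. Crossing a boundary means that termination will be considered, so these are trigger probabilities, not probabilities of automatic stopping. The change should be made: continuing DSMB review reduces the consequence of the gap but does not give the board an agreed trigger.

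**What to change.** In section 12.2.1:
1. State the posterior cut-off, for example P(DLT rate > 30%) ≥ 0.77.
2. State the monitoring unit: toxicity on HCQ + EVE is monitored with Arms C and D counted together from the first combination dose. Section 10.11 counts enrolled patients, but Arm D patients spend their first 12 weeks untreated, so the two sections should be aligned.
3. List boundaries up to the maximum planned for that unit. At a 0.77 cut-off these are 7/18, 8/21, 9/24, 10/27 and 11/30. If the sponsor takes the lowest listed value, 0.775, they are 8/18, 9/21, 10/24, 11/27 and 12/30.
4. Report the trigger probabilities at 20%, 30% and 40% beside the table, so that the DSMB sees the cost as well as the gain.

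The choice of cut-off is the sponsor's; the five existing lines are unchanged under either value. The cost is wording and a longer table, plus more triggers at acceptable rates: 19.5% to 21.3% at a 20% rate and 46% to 55% at the 30% target with the 0.77 table.

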12.2.2 Secondary Endpoints

The secondary endpoints are tolerability/toxicity and the measured effect of the investigational therapy on DTCs in patients with measureable DTCs at baseline and the comparison of this effect to that in a control population. Because this is proof-of-concept, sample sizes are not sufficient to address long-term recurrence risk. Randomization is being performed to minimize uncontrolled confounding.

We will define “response” for each patient as a 50% or greater decrease in DTC number at each treatment time point compared to baseline. A treatment arm will be considered successful if at least 3 of 15 patients experience this predefined response endpoint. This strategy is being used to provide preliminary estimates of effect on DTCs and to assess whether one or more treatment approaches has sufficient activity to be considered in a larger study powered for relapse-free survival. We anticipate that the baseline variability in DTC measurement will lead to no more than a 4% response rate in the absence of treatment (null rate). While the trial is powered for feasibility, 15 patients provide approximately 80% power to detect a response rate of 20%, warranting further study of the treatment strategy evaluated in this patient population and clinical setting.

We will also estimate, within each treatment group, the % change in BM-DTC number, defined as the difference between BM-DTCs enumerated at 6 months and at baseline, divided by the number at baseline; we will compare this quantity across treatment groups using simple regression analyses with indicator variables for the three active treatments compared to the delayed treatment. While the trial is powered for feasibility, rather than detection of change in BM-DTCs across treatment group, 15 patients per group will provide 80% power (using a two-group t-test with a two-sided alpha level of 0.05) to detect a decrease in BM-DTCs of approximately 1 standard deviation between any two groups and will provide important preliminary data for designing future trials.

Because of tumor heterogeneity, the natural history of recurrence varies substantially between breast cancer subtypes. We have elected not to expand the

sample size to evaluate subtypes individually in this feasibility pilot, but expect that we will enroll a mix of patients across subtypes that will shed light on variability in DTCs by subtype in an exploratory fashion.

In addition, we will estimate the 3-year relapse-free survival (RFS) of patients enrolled on the trial. Since this is a proof-of-concept and safety trial, we have elected not to power the trial for this endpoint, but anticipate collecting valuable information to inform and power a subsequent definitive trial powered for this endpoint.

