	
discontinued for lack of feasibility, the trial may continue enrolling to those arms that remain feasible.
 
Toxicity will be assessed using NCI CTCAE v4 criteria. Patients who drop out before completing cycle 6 for reasons other than grade 3/4 toxicity will be replaced. With 15 patients per group, an exact 95% confidence interval around the feasibility and toxicity rates will be no more than 0.52 units wide.
 
We will define “response” for each patient as a 50% or greater decrease in DTC number at each treatment time point compared to baseline. A treatment arm/regimen will be considered successful if at least 3 of 15 of patients experience this predefined response endpoint.
 
We will also estimate, within each treatment group, the % change in DTC number. While the trial is powered for feasibility, rather than detection of change in DTCs across treatment group, 15 patients per group will provide 80% power (using a two-group t-test with a two-sided alpha level of 0.05) to detect a decrease of approximately 1 standard deviation and will provide important preliminary data for designing future confirmatory trials.

--	---

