5.2 Screening Phase

Patients found to have detectable DTCs by immunohistochemistry, through the PENN-SURMOUNT Screening study (UPCC 28115; IRB# 824098) or other studies will be screened for trial participation during the screening phase. This will include assessments of medical history, overall physical condition, physical exam, baseline laboratory studies, and symptom-directed imaging (if applicable) to rule out the presence of overt metastatic disease, per NCCN guidelines. Patients will undergo a baseline bone marrow aspirate if their prior bone marrow aspirate detecting DTCs occurred > 6 months prior to the screening phase. If a bone marrow aspirate positive for DTCs occurred ≤ 6 months prior to screening, this will not be repeated, and the prior DTC count will provide the baseline DTC assessment.

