5.3 Treatment Phase

Patients who have signed informed consent will be randomized to start the treatment phase. The study arms are described below. Patients are assessed for adverse events, toxicity and laboratory abnormalities at each study visit. Bone marrow aspirate will be performed at the end of the third cycle of observation, between D23-28 (Arm D), at the end of 3 cycles of therapy, between D23-D28 (all arms), after 6 cycles of therapy, between D23 of C6 and within 21 days of the last dose of C6 (all arms), and, if patient continues on treatment, at the end of C12, between D23 of C12 and within 21 days of the last dose of C12. After the first 6 cycles of study therapy, patients will stop all study medication and proceed with

bone marrow evaluation per protocol. When the results are available it will be determined whether or not the patient will continue on study therapy. If continuing on study therapy, Cycle 7 must be initiated within 45 days after the last dose of cycle 6. Results from the end of C3 and end of observation bone marrow tests will not be returned to patients. Patients, however, will receive the results of the end of C6 and, if applicable and if desired, end of C12 bone marrow tests. End of C6 and, if applicable, end of C12 bone marrow DTC results disclosure can be done remotely over the phone if deemed appropriate by the PI or treating physician.

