11.1.2 Evaluable for objective response

Only those patients who have measureable DTCs present at baseline, have received at least one cycle of therapy, and have had their disease re-evaluated at the 24 week timepoint will be considered evaluable for response. These patients will have their response classified according to the definitions stated below. We will report on both the "intent-to-treat" population and the evaluable population per the above criteria in order to fully determine whether the interventions are both feasible and showing sufficient evidence of activity to take forward to a larger phase III trial powered for relapse-free survival (RFS).

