11.1.3 Measurable Disease

Patients enrolled on the CLEVER trial will have completed surgery for their primary breast tumor and be free of overt metastatic disease. Thus there is no tumor to measure for the effect of the study therapy. Rather, the goal of this trial is to eradicate minimal residual disease, in the form of disseminated tumor cells (DTCs) that are present in the bone marrow. Therefore, bone marrow DTCs constitute the "measurable" disease in this trial. A patient will be classified as having "measurable disease" if at least 1 disseminated tumor cell (DTC) is detected

in 5 ml of bone marrow aspirate by immunohistochemistry, as described in section 13.2.1.

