11.2.2 Response Criteria

Response in this trial will be performed in all patients, and is defined by the change in detectable DTC number (# cell/5 ml marrow aspirate) from baseline to each timepoint. We will define “response” for each patient as a 50% or greater decrease in DTC number at each treatment time point compared to baseline. The interventional arm will be considered successful if at least 20% of patients experience this predefined response endpoint. We anticipate that the baseline variability in DTC measurement will lead to no more than a 4% response rate in the absence of treatment (null rate). The efficacy objective of this trial (a secondary objective) is to evaluate the preliminary efficacy of EVE, HCQ or the combination in reducing or eliminating breast cancer DTCs, and provide estimates of effect for future definitive trials. The primary measure of efficacy in this trial is change in the number of detectable disseminated tumor cells (DTCs) in the bone marrow of patients on study. DTCs will be detected from 5 ml of bone marrow extracted from the posterior iliac crest at baseline (pre-treatment), after 3 cycles, 6 cycles, and 12 cycles (if applicable) of study treatment, and at 6 months after the last dose of study treatment (optional).

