13.2 Laboratory Assays

13.2.1 DTC Assessment by Immunohistochemistry

The presence of DTCs in the marrow by IHC is an integral biomarker required on this study for eligibility. In addition, this assay will be used to quantitate DTC response to therapy. The gold standard method for DTC assessment is immunohistochemistry (IHC), and all samples obtained during this trial will be subjected to IHC assessment. IHC to detect DTCs will be performed using the method adapted from Janni⁴ and Naume¹⁴. This well-established assay, which has been used both in prior prognostic studies and to determine trial eligibility for additional adjuvant chemotherapy¹⁴, has been replicated within the Research Pathology Laboratory of the University of Pennsylvania under the direction of [name], a co-investigator on this proposal, and subsequently implemented in our CLIA laboratory for clinical use. Briefly, 5 ml of a bone marrow aspirate sample drawn from the iliac crest under anesthesia and collected in an anti-coagulated tube containing EDTA will be stored at room temperature and processed within 24 hours. Density centrifugation using Lymphoprep will be performed and mononuclear cells (MNCs) will be harvested, washed and resuspended to 2.5×10^6 cells/ml. Cytospin slides will then be prepared from the cell suspension using a cytocentrifuge and slides will be fixed in 95% alcohol before immunostaining on a Leica Bond III autostainer. An anti-pancytokeratin monoclonal antibody will be used to screen for the presence of DTCs in the bone marrow aspirate sample. Cytospin slide containing only Hs578T cancer cell line will be used as a negative control, and a positive control containing pure MCF7 cancer cell line will be included in each run together with an antibody isotype negative control. Each cytospin will be prepared with 1×10^6 MNCs and a total of 5×10^6 cells will be evaluated per patient. Cytospin slides will be reviewed by [name] and [name] and reported. The presence

of one or more pancytokeratin positive cells with appropriate morphology of a tumor cell will be reported as positive according to the Consensus Committee morphological criteria published by Fehm⁸ and the Naume trial¹⁴. Additional cytospin slides will be prepared and stained in cases displaying atypical or indeterminate morphology.

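### The 3-of-15 DTC success rule rests on an untreated response rate of at most 4% that has no data behind it and takes no account of Arm D; its power at a 20% response rate is 60%, not about 80%

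*Protocol*

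**What the plan says.** Protocol 12.2.2 defines response as a fall of at least 50% in DTC count from baseline, at each treatment time point. The Study Summary gives the verdict: "A treatment arm/regimen will be considered successful if at least 3 of 15 of patients experience this predefined response endpoint". Section 12.2.2 repeats it, and section 11.2.2 puts it as a proportion: "The interventional arm will be considered successful if at least 20% of patients experience this predefined response endpoint". Section 12.2.2 uses the result to judge whether a regimen is active enough to be considered for a larger study powered for relapse-free survival.

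The benchmark, in sections 11.2.2 and 12.2.2, is that "baseline variability in DTC measurement will lead to no more than a 4% response rate in the absence of treatment (null rate". Neither place cites repeat-aspirate data, a count distribution or a source. Section 12.2.2 adds that 15 patients give roughly 80% power at a 20% response rate.

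Four other provisions bear on the rule:

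- **Entry count.** Section 11.1.3 counts disease as measurable "if at least 1 disseminated tumor cell (DTC) is detected" in 5 ml of marrow. Section 13.2.1 says that the presence "of one or more pancytokeratin positive cells with appropriate morphology of a tumor cell will be reported as positive".
- **Baseline.** Under section 5.2, if the positive aspirate is no more than 6 months old at screening, it is not repeated and "the prior DTC count will provide the baseline DTC assessment".
- **Arm D.** Section 7.1 observes Arm D for 12 weeks before combination therapy. Section 5.3 schedules marrows "at the end of the third cycle of observation, between D23-28 (Arm D), at the end of 3 cycles of therapy", so an untreated repeat count exists at 3 months but not at week 24.
- **Deciding visit.** Section 11.1.2 requires that patients "have had their disease re-evaluated at the 24 week timepoint will be considered evaluable for response", whereas sections 11.2.2 and 12.2.2 refer to each time point.

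**The concern.** The verdict compares an arm with a fixed number, and everything depends on whether that number is right. A patient who enters on one cell counts as a responder if the next sample shows none. Where the count that qualified the patient also serves as baseline, selection on a positive result makes a later fall more likely (regression to the mean). Falls of 50% or more without drug effect are therefore possible, and the documents do not let anyone say how common they are. Section 7 itself still lists assay reproducibility as something to be analysed.

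The trial has a randomised untreated group that could answer this at 3 months, but its result does not enter the rule. An inactive regimen could be put forward for a larger trial on measurement noise. In the other direction, overstated power would make a failure to reach 3 of 15 look more informative than it is.

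Two gaps also stop the rule from giving a unique answer. The deciding visit is not fixed. For the combination, the 15 patients are not defined: section 7.1 closes Arm C at Amendment 7 and sends its patients to Arm D, section 12.2.1 allows Arms C and D to be pooled for feasibility, and section 12.2.2 is silent on pooling for response.

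**Working it through.** **Inputs.** n = 15, cutoff 3, null rate at most 0.04, alternative 0.20, stated power about 80% (all from section 12.2.2). The protocol states neither an alpha nor a false-success rate for this rule.

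**1. Stated power.** For X ~ Binomial(15, p), P(X ≥ 3) = 1 − P(0) − P(1) − P(2).

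- At p = 0.20: 1 − 0.0352 − 0.1319 − 0.2309 = **0.602**. The stated 80% does not reproduce.
- A cutoff of 2 gives 1 − 0.0352 − 0.1319 = 0.833. At p = 0.04, however, that cutoff passes an inactive arm with probability 1 − 0.5421 − 0.3388 = 0.119.
- A normal approximation gives 0.771 at one-sided alpha 0.05 and 0.822 at one-sided 0.10, but neither describes the 3-of-15 rule.
- With a cutoff of 3, a power of 80% needs a true response rate of about 26.5%.

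**2. False success.** At p = 0.04: 1 − 0.5421 − 0.3388 − 0.0988 = **0.0203**. This figure is computed here and is not in the protocol. Because the tail probability rises with p, 2.0% is the maximum for any null up to 4%.

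| True untreated response rate | P(at least 3 of 15) |
|---|---|
| 2% | 0.3% |
| 4% | 2.0% |
| 5.7% | 5.0% |
| 8% | 11% |
| 10% | 18% |
| 20% | 60% |

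**3. Could counting noise exceed 4%?** This is an illustration only, because the documents give no count distribution. Assume that baseline and follow-up counts are independent Poisson with the same mean, baseline is at least 1, and the drug has no effect. A response is a follow-up count of no more than half the baseline count.

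| Assumed mean count | Null, one visit | False success | Null, months 3 and 6 both required | False success |
|---|---|---|---|---|
| 3 | 28% | 84% | 11% | 22% |
| 5 | 19% | 55% | 6% | 5% |
| 10 | 8% | 13% | 2% | 0.2% |
| 15 | 4% | 2% | 0.5% | <0.1% |

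Under this model the 4% is met at a mean of about 15 (one visit) or 6 (both visits). The table shows that 4% may or may not be right, and that the undefined visit rule changes the answer.

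**4. What Arm D can and cannot show.** It cannot confirm 4%: with 0 of 15 untreated responders the exact two-sided 95% upper limit is 1 − 0.025^(1/15) = 21.8%. It can expose a badly wrong null: if the untreated rate were 20%, two or more of 15 would respond with probability 0.83.

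**5. Precision of a comparison with Arm D.** For 3/15 against 0/15 the difference is 20 points, with a Newcombe 95% interval of −4 to 45. With 15 per group, the chance that the lower limit exceeds 0 is 21% for true rates of 20% against 4%. It is 2.5% when both rates are 20%, where 3 of 15 is reached 60% of the time.

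**The case against.** The strongest reply is that the plan does not neglect its control group. Section 2.2.2 lists the 3-month change in Arm D against any treatment. Section 12.2.2 names comparison with a control population and plans a regression of percent change against delayed treatment. The SAP's Bayesian Poisson model reports each regimen against observation alone at C3 and does not mention the 3-of-15 rule. Section 7 enlarges Arm D precisely to obtain more repeat assessments. A reader might infer from the concern that activity will be judged without any control, and the documents do not support that. What stands is narrower: none of these analyses governs the 3-of-15 verdict, and the regression in section 12.2.2 uses 6-month counts, when Arm D has no untreated value.

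A reader might also infer that the 4% is wrong, or that false success is 55% or 84%. The documents do not show this either. Those figures need an assumed mean of 5 or 3 cells, and the same model gives about 2% at a mean of 15.

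The rule is also a secondary criterion in a pilot powered for feasibility, meant to give preliminary estimates. That limits the harm, but section 12.2.2 still attaches a decision about further study to it.

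Finally, replacing the rule by a test that the difference from Arm D excludes zero would be costly: at 20% against 4% it would succeed 21% of the time, against 60% for 3 of 15. That objection is sound, and such a replacement is not proposed.

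**Conclusion.** The point holds in limited form. The untreated response rate of at most 4% is an expectation without data in the documents, and the success rule makes no use of the untreated Arm D marrow already scheduled. False success is at most 2.0% if the expectation is right. It rises to 5% at a null of 5.7%, 18% at 10% and 60% at 20%. These figures assume 15 independent patients with a common response probability and one defined response per patient. Where the true null lies is unknown, and it may be below 4%.

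The power error does not depend on the null: 3 of 15 has 60% power at a 20% response rate, about 20 points below the stated figure.

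The matter should be fixed. It does not touch the primary feasibility endpoint, and it is no reason to abandon the week-24 response.

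**What to change.** 1. Treat 3 of 15 (20%) as descriptive rather than as a stand-alone verdict of activity. State which visit decides response and which patients form the combination denominator.
2. Beside it, report Arm D's observed rate of a 50% or greater fall at the end of observation, and the C3 difference for each active arm with a 95% interval, all from the screening baseline. For Arm C, use Arm D patients randomised while Arm C was open. For Arms A and B, stratify by randomisation before or after Amendment 7, because the share sent to Arm D changes then. Do not call an arm active on 3 of 15 if Arm D's untreated rate is similar.
3. Correct the power statement in section 12.2.2 to about 60% at a 20% response rate.
4. Keep the week-24 response as planned, reported without a control comparison because Arm D has no untreated week-24 value.

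**Cost.** The marrows are already scheduled, so no visits or samples are added. The protocol and SAP text would need amending. The intervals will be wide, as the 3/15 against 0/15 example shows, so claims of activity become more cautious.
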